2. TYPE OF PLANNED ANALYSIS

2.1. DMC Analyses

An external multidisciplinary data monitoring committee (DMC) will review the progress of the study and perform interim reviews of safety data and provide recommendation to Gilead about whether the nature, frequency, and severity of adverse effects associated with study treatment warrant the early termination of the study in the best interests of the participants, whether the study should continue as planned, or the study should continue with modifications.

Specific activities of the DMC will be defined by a mutually agreed charter, which will define DMC membership, conduct and meeting schedule.

2.2. Final Analysis

After all subjects have completed through the post-treatment week 24 visit or have prematurely discontinued from the study, outstanding data queries have been resolved, and the database has been cleaned and finalized, the final analysis of the data will be performed.

3. GENERAL CONSIDERATIONS FOR DATA ANALYSES

Analysis results will be presented using descriptive statistics. For categorical variables, the number and percentage of subjects in each category will be presented; for continuous variables, the number of subjects [n], mean, standard deviation [SD] or standard error [SE], median, first quartile [Q1], third quartile [Q3], minimum, and maximum will be presented.

Data collected in the study will be presented in by-subject listings for all subjects in the Safety Analysis Set, unless otherwise specified. All by-subject listings will be presented by subject identification (ID) number in ascending order, unless otherwise specified.

3.1. Analysis Sets

Analysis sets define the subjects to be included in an analysis. Analysis sets and their definitions are provided in this section. The number of subjects eligible for each analysis set will be provided. Subjects who were excluded from Safety and Full Analysis Sets will be provided in a by-subject listing with reasons for exclusion.

3.1.1. All Enrolled Analysis Set

All Enrolled Analysis Set includes all subjects enrolled in the study after screening. All analyses based on the All Enrolled Analysis Set will be performed according to the treatment group to which subjects were enrolled.

3.1.2. Full Analysis Set

The Full Analysis Set (FAS) includes HCV infected subjects who were enrolled into the study and received at least one dose of study drug. The study drugs in this study include SOF and RBV. Subjects are grouped within the FAS by the treatment group to which they were enrolled.

This is the primary analysis set for efficacy analyses.

3.1.3. Safety Analysis Set

The Safety Analysis Set includes all subjects who took at least 1 dose of study drug (i.e. SOF and RBV). Subjects will be grouped according to the treatment they actually received.

This is the primary analysis set for safety analyses.

3.1.4. Pharmacokinetic Analysis Set

PK Lead-in Phase Intensive PK Analysis Set

The PK Lead-in Phase Intensive PK Analysis Set includes all PK Lead-in Phase subjects who received at least one dose of study drug and for whom at least one non-missing PK concentration data is available from the PK Lead-in Phase intensive sampling. This is the primary analysis set for PK Lead-in Phase intensive PK analysis.

Population PK Analysis Set

The Population PK Analysis Set includes all enrolled subjects who received at least one dose of study drug and for whom at least one non-missing PK concentration data is available from the PK sampling. This is the primary analysis set for the Population PK modeling and PK exposure analyses.

The PK Analysis Set is equivalent to Population PK Analysis Set.

3.2. Subject Grouping

For analyses based on the All Enrolled Analysis Set or FAS, subjects will be grouped according to the treatment to which they were enrolled. For analyses based on the Safety Analysis Set, subjects will be grouped according to the actual treatment received. The actual treatment received is defined as the enrolled treatment except for subjects who received treatment that differs from the enrolled treatment for the entire treatment duration. In this case, the actual treatment received is defined as the treatment received for the entire treatment duration.

Specifically, efficacy and safety analyses will be performed according to age group and HCV genotype in the following treatment groups:

Table 3-1. Treatment Groups

12 to < 18 Years Old SOF(400mg)+RBV		3 to < 12 Years Old SOF(200mg or 150mg)+RBV	
GT-2 12 Weeks (N =)	GT-3 24 Weeks (N =)	GT-2 12 Weeks (N =)	GT-3 24 Weeks (N =)
6 to < 12 Years Old SOF(200mg)+RBV		3 to < 6 Years Old SOF(200mg or 150mg)+RBV	
GT-2 12 Weeks (N =)	GT-3 24 Weeks (N =)	GT-2 12 Weeks (N =)	GT-3 24 Weeks (N =)

GT = genotype

Subjects in the 3 to < 6 years of age group will have additional selected efficacy and safety analyses performed according to baseline weight and HCV genotype in the following subgroups:

Table 3-2. Subgroups for Selected Analyses in 3 to < 6 years of Age

3 to < 6 Years Old			
GT-2 12 Weeks		GT-3 24 Weeks	
< 17 kg SOF(150mg)+RBV (N =)	>= 17 kg SOF(200mg)+RBV (N =)	< 17 kg SOF(150mg)+RBV (N =)	>= 17 kg SOF(200mg)+RBV (N =)

GT = genotype

3.3. Strata and Covariates

This study does not use a stratified randomization schedule for enrolling subjects. No covariates will be included in efficacy and safety analyses.

3.4. Examination of Subject Subsets

The efficacy endpoint SVR12 will be analyzed for the following subsets:

- sex (male, female)
- race (black, non-black)
- ethnicity (hispanic or latino, non-hispanic or latino)
- baseline HCV RNA ($< 800,000$ IU/mL, $\geq 800,000$ IU/mL)
- baseline weight (\leq median, $>$ median)
- baseline ALT ($\leq 1.5 \times$ ULN, $> 1.5 \times$ ULN)
- IL28B (CC, non-CC [further broken down to CT, TT])
- prior HCV treatment experience (treatment naive, treatment experienced)
- Interferon (IFN) eligibility (IFN-eligible, IFN-ineligible)
- most recent response to prior HCV treatment (non-response, relapse/breakthrough, IFN-intolerant) for treatment experienced subjects
- study treatment status (completed study treatment, discontinued study treatment)
- adherence to study regimen ($< 80\%$, $\geq 80\%$).

3.5. Missing Data and Outliers

3.5.1. Missing Data

In general, missing data will not be imputed unless methods for handling missing data are specified.

For missing last dosing date of study drug, imputation rules are described in Section 3.7.1. The handling of missing or incomplete dates for adverse event (AE) onset is described in Section 7.1.5.2, and for prior and concomitant medications in Section 7.9.

For analyses of categorical HCV RNA data, missing posttreatment HCV RNA data will have the missing data imputed. Missing on-treatment HCV RNA will have the missing data imputed up to the time of the last dose (for on-treatment displays). If the study day associated with the last dosing date is greater than or equal to the lower bound of a visit window, and the value at the visit is missing, the value will be imputed. If the study day associated with the last dosing date is less than the lower bound of a visit window then the on-treatment value at that visit will remain missing.

If a data point is missing and is preceded and followed in time by values that are “< LLOQ target not detected (TND)”, then the missing data point will be set to “< LLOQ TND”. If a data point is missing and preceded and followed by values that are “< LLOQ detected”, or preceded by “< LLOQ detected” and followed by “< LLOQ TND”, or preceded by “< LLOQ TND” and followed by “< LLOQ detected”, then the missing value will be set to “< LLOQ detected”. In these situations the data point will be termed a bracketed success; otherwise, the data point will be termed a bracketed failure (i.e. \geq LLOQ detected). If a data point is missing and is not bracketed, the missing data point will also be termed a failure (i.e. \geq LLOQ detected) except for SVR24, which will be imputed according to SVR12 status. Success for SVR12 who have no further HCV RNA measurements collected will be counted as a success for SVR24 due to the high correlation between these 2 endpoints.

For the analyses of continuous HCV RNA efficacy data, when and only when a missing HCV RNA value is imputed as < LLOQ TND or < LLOQ detected according to the imputation rule described above, the corresponding continuous value will be imputed to LLOQ - 1 IU/mL. No other imputation will be performed for continuous HCV RNA data.

In the analysis of the PedsQL™ Pediatric Quality of Life Inventory V4.0 Short Form (SF15) questionnaire, missing data at on-treatment visits and posttreatment follow-up Week 12 (FU-12) visit will not be imputed. Last posttreatment observation carried forward will be used for imputation of missing data at posttreatment follow-up Week 24 visit.

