### 9.2.2. Data Handling Conventions

Natural logarithm transformation for key PK parameters, such as  $C_{max}$  and  $AUC_{tau}$ , will be applied for pharmacokinetic analysis.

The PK concentration values below the limit of quantitation (BLQ) will be treated as zero for the determination of summary and order statistics. Individual values that are BLQ will be presented as “BLQ” in the concentration data listing and will be excluded in any calculation of geometric means or ratios. For the presentation of summary and order statistics, if at least 1 subject has a concentration value BLQ for the time point, then the minimum value will be displayed as “BLQ”. If more than 50% of the subjects have a concentration data value BLQ for the time point, then the minimum and median values will be displayed as “BLQ”. If all subjects have concentration data values BLQ for the time point, then all order statistics (minimum, first quartile [Q1], median, third quartile [Q3], maximum) will be displayed as “BLQ”.

Missing data can have an impact upon the interpretation of the trial data. Other than the endpoints discussed below, in general, values for missing data will not be imputed.

For the analysis of post-baseline categorical efficacy endpoints, if a data point is missing and is preceded and followed in time by values that are deemed successes, then the missing data point will be termed a success; otherwise the data point will be termed a failure.

Any subject with missing data due to premature discontinuation of the study medication will be considered a failure at the time points subsequent to the date of discontinuation. If no HCV RNA values are obtained after the last dose of study medication, the subject will be considered a treatment failure for the SVR endpoints.

Where appropriate, safety data for subjects that did not complete the study will be included in summary statistics. For example,

- If a subject received study medication, the subject will be included in a summary of adverse events according to the treatment received; otherwise, if the subject is not dosed then they will be excluded from the summary.

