### **9.7. Quality of Life Analysis**

The data from PedsQL™ Pediatric Quality of Life survey will be summarized by visit and age group and overall.

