**Appendix Table 3. Treatment Phase: Post Treatment Visits Following Primary Study**

	4 Weeks Post Treatment	12 Weeks Post Treatment	24 Weeks Post Treatment
Clinical Assessments			
Vital Signs, Body weight and Height	X	X	X
Symptom-directed Physical Exam	X	X	X
AEs	X	X d	X d
Concomitant Medications	X		
Quality of Life Survey a		X	X
Tanner Pubertal Stage Assessment		X	X
Bone Age Assessment			X
Pregnancy Prevention Counseling c	X	X	
Laboratory Assessments			
Hematology, Chemistry	X	X	
HCV RNA	X	X	X
Viral Sequencing b	X	X	X
Urine Pregnancy Test e	X	X	X

a Quality of life survey will be completed by all subjects at 12-Week and 24-Week Post Treatment visits if a site is approved to use the survey. Subject is to review questionnaire with a parent/guardian and write/mark answers directly onto the questionnaire.

b Plasma samples will be collected and stored for potential HCV sequencing and other virology studies

c Female subjects of childbearing potential should be provided with Urine Pregnancy Test Kits, instructed on their use and requested to continue to self-monitor for pregnancy for 6 months after their last dose of RBV. If required by regulations, additional pregnancy tests beyond 6 months may be added. The subject should be contacted every 4 weeks and asked to report results of the urine pregnancy tests. If a positive urine pregnancy test is reported, the subject should return to the clinic for a serum pregnancy test.

d At Post Treatment Week 12 and 24, only SAEs will be captured

e Including partner pregnancy prevention for male participants (subjects 12 to < 18 years of age and subjects < 12 years of age at the discretion of the Investigator based on subject's pubertal status).

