7.7. Tanner Pubertal Stage Assessment

The Tanner stages will be used to evaluate the onset and progression of pubertal changes. Females will be rated for pubic hair growth and breast development, and males will be rated for pubic hair growth and genitalia development. The Tanner stages (Pubic Hair and Breasts for female; Pubic Hair and Genitalia for male) at EOT, FU-12 and FU-24 visit will be summarized by baseline Tanner stages using frequency count and percentage by sex overall and within each treatment group.

7.8. Pediatric Quality of Life (PedsQL™ SF-15) Questionnaires, Including Neuropsychiatric Examination by Emotional Function Domain

The PedsQL™ Pediatric Quality of Life Inventory V4.0 Short Form (SF15) will be completed at Day 1, EOT (Week 12 for genotype 2 subjects, Week 24 for genotype 3 subjects, or at Early Termination, if applicable), 12-Week Post-Treatment, and 24-Week Post-Treatment visits. Each survey accompanied by the respective parent proxy survey will be administered to the subject and their parent/legal guardian (with the exception of the Toddlers Report which will only be completed by the parent/guardian) for the current age group at the time of survey administration.

The transformed scale scores (0 to 100 scale) at baseline, EOT (Week 12 for genotype 2 subjects, Week 24 for genotype 3 subjects, or at Early Termination, if applicable), 12-Week Post-Treatment, and 24-Week Post-Treatment visits and change from baseline, change from EOT to posttreatment will be presented for each of the 4 domains of the SF-15 (physical functioning, emotional functioning, social functioning, and school functioning), and the Total Score. Scoring of the SF15 scales will be performed as described in Scaling and Scoring of the Pediatric Quality of Life Inventory™ (PedsQL™) by James W. Varni. A Wilcoxon signed rank test will be used to explore within treatment group changes in status from baseline to EOT (Week 12 for genotype 2 subjects, Week 24 for genotype 3 subjects, or at Early Termination, if applicable), and from EOT to each of the posttreatment time points. Results (p-values) will be presented, but should be interpreted with caution as multiple endpoints are being tested, and the study has not been powered to test these exploratory endpoints. Plot of the mean \pm SD of change from baseline in SF15 summary scores will be presented.

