7.11. Changes From Protocol-Specified Safety Analyses

There are no deviations from the protocol-specified safety analyses.

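### PedsQL scores missing at post-treatment Week 24 are filled, without explanation, with the last post-treatment score (in practice Week 12), which pulls the Week 24 change toward the Week 12 change

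*SAP*

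**What the plan says.** PedsQL is scheduled at Day 1, end of treatment (EOT) or early termination, and post-treatment Weeks 12 and 24 (protocol 6.6.13). Protocol Appendix Table 3 confirms the two post-treatment surveys: "Quality of life survey will be completed by all subjects at 12-Week and 24-Week Post Treatment visits", subject to the site being approved to use the survey.

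SAP 3.5.1 sets two rules for gaps. At the earlier visits, "missing data at on-treatment visits and posttreatment follow-up Week 12 (FU-12) visit will not be imputed". At the last visit, "Last posttreatment observation carried forward will be used for imputation of missing data at posttreatment follow-up Week 24 visit". The SAP's general default in the same section is "In general, missing data will not be imputed unless methods for handling missing data are specified".

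Protocol 9.2.2 states its own default: "Other than the endpoints discussed below, in general, values for missing data will not be imputed". The exceptions that follow are post-baseline categorical efficacy endpoints including SVR, screening values used for missing baseline laboratory or vital-sign results, and HCV RNA below LLOQ. PedsQL is not among them. Protocol 9.7 plans only that "The data from PedsQL™ Pediatric Quality of Life survey will be summarized by visit and age group and overall".

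SAP 7.8 summarises FU-24 scores and their changes from baseline and from EOT. It also runs Wilcoxon signed-rank tests within treatment group from baseline to EOT "and from EOT to each of the posttreatment time points". It calls these tests exploratory and unpowered and advises caution with the p-values.

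**The concern.** One visit of one instrument is treated differently from all its other visits, and the SAP does not say why. The contrast with HCV RNA is plain. Where SVR12 status is carried to SVR24, SAP 3.5.1 gives a reason (high correlation between the two). SAP 6.2.2 then restricts the SVR12/SVR24 concordance table to observed data and separates observed from imputed results at each follow-up visit. PedsQL has none of these safeguards.

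At stake is what the FU-24 result means. It is meant to show quality of life 24 weeks after treatment, but part of it would be the Week 12 result repeated, with nothing in the output to show how much. If quality of life moves between Weeks 12 and 24, the FU-24 estimate is biased. A change that has disappeared could still be reported, or a late improvement understated.

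**Working it through.** The plan gives no PedsQL missing rate, SD, expected change or sample size, so there is no stated figure to reproduce. The effect and missing-rate inputs below are assumptions.

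**1. What is carried.** Only Weeks 12 and 24 are scheduled after treatment, so the carried value is normally Week 12. Subjects without any post-treatment survey have nothing to carry and stay missing. One ambiguity remains: SAP Table 3-4 gives no PedsQL window, so a late early-termination survey might also count as post-treatment.

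**2. Effect on the mean.** Let d be the share of FU-24 values that are carried, with missingness unrelated to outcome. Then:

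expected FU-24 mean change = (1−d) × true FU-24 change + d × true FU-12 change

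*Change that fades* (0.5 SD at FU-12, 0 at FU-24):
- d = 5%: 0.95 × 0 + 0.05 × 0.5 = 0.025 SD
- d = 10%: 0.90 × 0 + 0.10 × 0.5 = 0.05 SD
- d = 20%: 0.80 × 0 + 0.20 × 0.5 = 0.10 SD
- d = 30%: 0.70 × 0 + 0.30 × 0.5 = 0.15 SD

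*Change that grows* (0.2 SD at FU-12, 0.5 SD at FU-24), d = 20%: 0.80 × 0.5 + 0.20 × 0.2 = 0.44 SD instead of 0.50 SD.

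**3. Effect on the test.** The EOT-to-FU-24 signed-rank test was simulated at the 0.05 level with normal changes of SD 1, FU-12/FU-24 correlation 0.5, values missing completely at random, and 2,000 runs. The Monte Carlo standard error near 5% is √(0.05 × 0.95 / 2000) ≈ 0.005. The two sizes tried were n = 50, the planned size of a whole age group, and n = 25. The tests run within treatment group, and SAP Table 3-1 splits age groups by genotype in proportions the plan does not give, so actual n may be below 50.

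Rejection rate for the fading change, where the true FU-24 change is 0:

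| Missing | n = 50, carried | n = 50, observed | n = 25, carried | n = 25, observed |
|---|---|---|---|---|
| 5% | 0.043 | 0.042 | 0.045 | 0.044 |
| 10% | 0.062 | 0.046 | 0.058 | 0.047 |
| 20% | 0.100 | 0.050 | 0.066 | 0.044 |
| 30% | 0.172 | 0.050 | 0.110 | 0.048 |

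For the growing change at n = 50 and 20% missing, the simulated mean is 0.438 SD carried against 0.496 SD observed. The rejection rates are almost the same, 0.835 and 0.842.

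**4. No change at either visit.** Carry-forward rejects in 0.045 to 0.056 of runs across all settings, so the test keeps its level.

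**5. Standard error.** With no change at either visit and equal SDs, carried and observed values have the same distribution, so the SE of the mean at n = 50 is 1/√50 = 0.141. Simulation under the same assumptions with 20% missing gave a mean reported SE of 0.141 and an empirical SE of 0.138, so no understatement appears.

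**The case against.** The strongest reply is that this rule is permitted and matters little. The protocol's text is a general default, not a ban, and 9.7 sets no missing-data rule for PedsQL. The SAP's own default allows imputation where a method is specified, and here one is. That stands: the SAP does not contradict itself, and the most that can be said is that it adds an unexplained rule the protocol does not provide for.

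A reader might go further and take SAP 7.11 ("There are no deviations from the protocol-specified safety analyses") to be false. The documents do not support that. The SAP places PedsQL in its safety section, but the protocol places it in 9.7, outside the safety analyses of 9.5. A line of disclosure would be helpful, but the statement is not shown to be wrong.

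A reader might also infer that carried scores are counted twice and that the SE is understated by 1 − √(1−d), about 2.5%, 5% or 11% at 5%, 10% or 20% missing. That does not follow. Each subject gives one pair per test, and a carried score is that subject's own change, which varies like any other. Steps 4 and 5 show no understatement and no general shift toward small p-values.

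Finally, observed-only analysis is unbiased here because the simulation assumes values missing completely at random, which the documents cannot establish. That also stands. But carry-forward is biased even in that favourable case whenever scores move after Week 12, and the SAP offers no argument that it does better otherwise. The SAP's caution on the p-values concerns multiplicity and power, so it does not alert a reader to carried scores.

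**Conclusion.** The point holds as a minor one. The FU-24 rule is unexplained, differs from every other PedsQL visit, and biases the FU-24 change toward the Week 12 change. The size depends on an unstated missing rate and on how far scores move between Weeks 12 and 24. At 5% missing it is negligible. At 20%, a 0.5 SD change that has gone by FU-24 shows as 0.10 SD, with a false-positive rate of about 10% at n = 50 or 7% at n = 25, against about 5% and 4% for observed scores. A change growing from 0.2 to 0.5 SD shows as 0.44 SD. These figures assume missingness unrelated to outcome. The rejection rates also assume correlation 0.5 and normal changes. PedsQL is exploratory, so no primary safety or key efficacy conclusion changes.

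**What to change.** Delete the carry-forward sentence from SAP 3.5.1 so that FU-24 is analysed on observed PedsQL scores like the other visits, and show n at each visit in the SAP 7.8 tables. If the sponsor wants to keep carry-forward, make it a labelled sensitivity analysis with a stated reason and the number of carried scores per treatment group, and note that the protocol does not provide for it. If the SAP is already final, SAP section 1 sends the change to the clinical study report.

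The cost is one sentence, a slightly smaller n at FU-24, and reliance on the subjects who completed that survey. No new data or procedures are needed.

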3.5.2. Outliers

Outliers will be identified during the data management and data analysis process, but no sensitivity analyses will be conducted. All data will be included in the data analysis.

